# Evaluating the safety and effectiveness of Sonova's self-fitting method for hearing aids

## 1 Background

As part of the FDA Reauthorization Act of 2017, the FDA was directed to establish an Over-The-Counter (OTC) hearing aid category, and the agency issued a proposed rule in October of 2021. The proposed rule addresses the conditions for sale of hearing aids, and includes certain requirements for device performance, safety, design, and labeling. The proposed category is intended for individuals age 18 and older, who have a mild to moderate hearing loss.

In advance of the final ruling, Bose submitted a De Novo application in 2018 for the SoundControl Hearing Aid, from which the FDA implemented a new classification product code: QDD-Self fitting Air Conduction hearing aid. This application was approved in October of 2018, and since that time, two additional devices have been submitted and approved under the QDD category: Jabra Enhance Plus (GN Resound) and BHA100 Series Braun Clear Hearing Aid (Kaz USA, Inc., a Helen of Troy company).

Sonova believes that OTC hearing aids can be a first step for many people who otherwise would not seek professional help for their hearing loss. This study is necessary to obtain clinical data supporting the safety and effectiveness of Sonova's self-fitting method, which will support an application for 510(k) clearance from the FDA. This study will use the HelloGO devices, which is the OTC/self fitting device developed by Sonova and currently only distributed in Australia.

## 2 Objectives

The primary effectiveness objective of this investigation is to demonstrate that individuals age 18+ with self-perceived mild to moderate hearing loss are able to achieve non-inferior APHAB-global benefit scores when using a device fit with Sonova's self-fitting method compared to the same device fit by a professional.

The secondary effectiveness objective of this investigation is to demonstrate that individuals age 18+ with self-perceived mild to moderate hearing loss are able to achieve non-inferior dB SNR (Signal-to-Noise Ratio) loss scores as measured by the QuickSiN test, when using a device fit with Sonova's self-fitting method compared to the same device fit by a professional.

## 3 Description of the investigational device

The HelloGO Hearing Device is a one-size-fits-most form factor designed for individuals 18 years of age and older, with mild to moderate hearing loss. Through a companion app called HelloGO Hearing, the end user can set-up their devices by selecting a sound profile in the app that is suitable for their level of hearing, or they can choose to purchase a "pro upgrade," where

they can have their devices fine-tuned through fitting software with a hearing care professional. In both scenarios the app also serves as a remote control.

The intended use of the HelloGO hearing devices is to amplify and transmit sound to the ears and hereby compensate for hearing loss. The devices used in this investigation will be the means by which to evaluate subjective and objective benefit of the self-fitting created by the end-user using the App, as compared to an HCP-created fitting following best practices.

The intended patient population for the HelloGO hearing device and the HelloGO app are individuals 18 years or older with self-identified mild to moderate hearing loss. As part of the screening process for this study, potential participants are required to undergo audiological testing to confirm mild to moderate hearing loss.

#### **4 Design of the clinical investigation**

This investigation is a randomized, double-blinded crossover study with two treatments (self-fitting vs. professional-fitting), two treatment sequences, and two periods. Treatments include a device fit by the user with Sonova's self-fitting method and the same device fit by a professional following clinical best practices. This is a non-inferiority study, comparing the self-fitting method to the professional fitting method, therefore, the professional fitting method will serve as the comparator and the control.

#### **5 Risks and benefits of the investigational device and clinical investigation**

There are minimal risks associated with both the investigational device and participating in the clinical investigation. Identified risks are no greater than those associated with the daily use and wear of approved, available hearing aids.

The benefits of participating in the investigation include the possibility of hearing sounds that have not been previously heard, such as speech and environmental sounds, which may improve communication in daily life. Additionally, participation in this study will help to inform future developments and improvements in hearing device technology.

Subjects experience the benefit of personal satisfaction for participating in research to improve hearing instrument technology, which has the potential to make future HelloGO use more convenient. Subjects will also be compensated for their time in participating in this study.

There are no known or anticipated risks to subject hearing ability associated with participation in the study. All sounds used in this study will be presented at safe listening levels.

While using HelloGO the following are possible occurrences:

- Cerumen impaction
- Discomfort, pain, or soreness
- Sweat or moisture accumulation in the ear canal or pinna
- A feeling of pressure or fullness in the ear
- Blisters, itching, sores, or rashes in the ear canal or pinna
- Headache
- Redness of tissue

The research personnel will review all of these risks with the subjects and answer any questions they have.

This is a non-significant risk study following the abbreviated IDE requirements set forth in 21 C.F.R. § 812.2 (b)(1). HelloGO is not a significant risk investigational device as defined in 21 C.F.R. § 812.3 (m).

## **6 Endpoints**

Primary effectiveness endpoint: Abbreviated Profile of Hearing Aid Benefit (APHAB) global benefit score, which is derived by subtracting the aided APHAB global score from the unaided APHAB global score. The APHAB is an externally developed and validated questionnaire that is available for use by both researchers and clinicians to assess hearing aid benefit (Cox and Alexander, 1995). The measure comprises 24 items distributed equally across four subscales ('Ease of Communication,' 'Reverberation,' 'Background Noise,' and 'Aversiveness'). These subscales were designed to assess the benefits of hearing aids for speech communication in a variety of listening environments, in addition to capturing the impact of bothersome loud sounds.

Secondary effectiveness endpoint: dB SNR loss score. QuickSiN, the testing procedure that measures dB SNR loss, is an adaptive test of an individual's ability to understand speech in noise. The test adapts the relative levels of noise and speech to determine the signal-to-noise ratio (SNR) at which the individual can correctly identify 50% of key words. This test was independently developed and validated and is available for use by clinicians and researchers (Killion, et al., 2004).

These outcomes closely match those of a recent study for a product cleared under the Self-Fitting Hearing Aid classification 510(k) K213424.

## **7 Inclusion and Exclusion Criteria**

Inclusion criteria for participant selection:

- 18-80 years of age
- Target 67-75% first-time hearing aid users, 25-33% experienced hearing aid users
- Mild to moderate bilateral hearing loss
- Ability to use a smartphone
- Fluent in English; ability to read and write in English
- Willing and able to provide informed consent
- Willing to upload smartphone app to personal phone

Exclusion criteria:

The presence of any one of the following exclusion criteria will lead to the exclusion of the subject:

- Self-reported ear-related pathology (otorrhea w/in 90 days, dizziness, sudden hearing loss or worsening of hearing w/in 90 days, otalgia)
- Visible deformity of the ear
- Chronic, severe tinnitus
- Unilateral hearing loss

## **8 Measurements and procedures**

This is a crossover design in which participants will spend two weeks wearing devices that are professionally programmed according to the participant's audiogram, and two weeks wearing devices that are entirely self fit. The order of fitting will be randomized in a 1:1 allocation ratio.

Participants will complete the QuickSiN speech test in all three conditions: unaided, aided with professional fitting, and aided with self-fitting. They will also complete the APHAB questionnaire in all three conditions.

Real Ear Aided Responses (REAR) will be measured following the initial fittings as well as at each follow up visit.

See table below for schedule of events.

Appointment	Trial Day	Variables recorded
1	1	
 
• Unaided APHAB
 
• Unaided QuickSiN
 
• Initial fittings for both treatments
 
• REAR for both treatments
 

2	2-7	N/A: First set of devices dispensed following a wash-out period
3	16-21	
 
• Adverse Event assessment
 
• APHAB with first treatment
 
• QuickSiN with first treatment
 
• REAR with first treatment
 
• Blinding assessment
 

4	30-35	
 
• Adverse Event assessment
 
• APHAB with second treatment
 
• QuickSiN with second treatment
 
• REAR with second treatment
 
• Blinding assessment
 

## 9 Statistical design and analysis

Sample size is driven by the difference in APHAB global benefit scores between self-fitting and the professionally-fitted hearing aid. Assuming that the average difference score,  $APHAB_{self} - APHAB_{prof}$  is -5.0, and the standard deviation of the difference score is 14, 40 subjects with APHAB global scores in both periods are needed to demonstrate with 90% power the non-inferiority against the margin of -12.5 using Mixed Model ANOVA, setting one-tailed  $\alpha=0.025$ .

Anticipating an attrition rate of no more than 10%, to minimize the impact of imputed data on the overall efficacy conclusion, 44 subjects will be enrolled and those randomized will enter into the Intent to Treat population.

In terms of examining safety, the proportion of subjects experiencing any Adverse Device Effect will be a key safety endpoint. A sample size of 40 provides a 95% Clopper-Pearson confidence interval with a half-width no wider than 0.133 when the observed sample proportion is 0.20 or less. In other words, we can be 95% confident that the true population proportion of Adverse Device Effects is no greater than 0.133 larger than the observed sample proportion when the sample size is 40 and the sample proportion is 0.20 or less.

Note that this sample size is slightly higher than that included in 510(k) K213424, which included the same endpoints and a similar crossover design.

The analysis populations are as follows:

Intent to Treat: All participants randomized.

Safety: All participants randomized who receive one or more study device kits.

Data will be entered immediately following participant completion of the assigned tasks. Unaided and both aided responses will be analyzed for each participant for the APHAB global benefit and dB SNR loss scores. The two aided conditions will be analyzed for non-inferiority as per the statistical plan.

The APHAB global benefit score recorded during the self-fitting will be compared to the APHAB global benefit score recorded during the professional-fitting by way of a 2-period, crossover, repeated measures mixed model, where APHAB score is the dependent variable, treatment sequence is the between-subjects factor, Period is the within-subjects factor and treatment (Self-Fit/Professional-Fit) is the repeated measures factor.

The hypotheses are:  $H_0: \mu_{\text{self}} - \mu_{\text{prof}} < -12.5$   $H_a: \mu_{\text{self}} - \mu_{\text{prof}} \geq -12.5$ ,

where  $\mu_{\text{self}}$  represents the mean APHABself score in the population and  $\mu_{\text{prof}}$  represents the mean APHABprof score in the population.

The observed treatment effect will be compared to the non-inferiority margin of -12.5 by way of pre-planned TEST or ESTIMATE statements using SAS PROC GLM or PROC MIXED.

The carryover effect will be tested by means of a RANDOM statement on the subject nested within sequence effect.

The planned analysis will be done by an expert biostatistician who has previous experience with FDA clinical trials.

The dB SNR loss score recorded during the self-fitting will be compared to the dB SNR loss score recorded during the professional fitting by way of a 2-period, crossover, repeated measures mixed model, where dB SNR loss score is the dependent variable, treatment sequence is the between-subjects factor, Period is the within-subjects factor and treatment (Self-fit/Professional-Fit) is the repeated measures factor.

The carryover effect will be tested by means of a RANDOM statement on the subject nested within sequence effect.

All analyses will be completed by an expert biostatistician who has previous experience with FDA clinical trials.

At each return lab visit, the sub-investigator A will notate any device deficiencies or possible adverse events as reported by the participant in the participant study folder.

If any AE are reported, the severity and scope will be reviewed and the study manager/sponsor, along with the PI will decide on the appropriate follow up.

Treatment-emergent Adverse Events will be attributed to the treatment condition (self-fit or professional fit) of the device being evaluated. The number and proportion of subjects reporting any Adverse Event, any Adverse Device Effect, any Serious Adverse Event, or any Serious Adverse Device Effect will be summarized by treatment condition and overall. The incidence of Adverse Events by AE term will be summarized by treatment condition and overall.

Missing aided APHAB global benefit scores and dB SNR loss scores for either visit 3 or 4 will be subjected to multiple imputation. Originally, missing data is assumed to be monotone and Missing at Random (MAR). Multiple imputation approach will follow fully-conditional specifica-

tion, Multiple Imputation of Chained Equations. There will be a minimum of 100 iterations of missing data, and these iterations will be combined according to Rubin's (1987) rules. Sensitivity analysis of the MAR assumption will be based on pattern-mixture model (Molenberghs and Kenward, 2007)

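### Does the 0.133 precision figure for Adverse Device Effects wrongly treat a half-width as the upper arm of the interval?

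*Combined protocol and SAP*

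**What the plan says.** Section 9 (Statistical design and analysis) calls the proportion of subjects with any Adverse Device Effect a key safety endpoint and gives two sentences on its precision.

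- The first: "A sample size of 40 provides a 95% Clopper-Pearson confidence interval with a half-width no wider than 0.133", subject to the condition "when the observed sample proportion is 0.20 or less".
- The second opens "In other words, we can be 95% confident that the true population proportion" and concludes that "the true population proportion of Adverse Device Effects is no greater than 0.133 larger than the observed sample proportion", under the same conditions of 40 subjects and an observed proportion up to 0.20.

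Later in Section 9 the safety summary is described: "The number and proportion of subjects reporting any Adverse Event, any Adverse Device Effect" and the serious categories are tabulated by treatment condition and overall. No interval is named there. The analysis set is "Safety: All participants randomized who receive one or more study device kits".

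**The concern.** The opening words of the second sentence present it as equivalent to the first. Half the width of an interval equals the distance from the estimate to the upper limit only if the interval is symmetric about the estimate. A Clopper-Pearson interval for a proportion below one half is not symmetric: the upper arm is longer than the lower. A half-width used as the upper arm therefore understates how high the true rate could be, and it errs in the direction that favours the device.

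At stake is how a reader judges the reassurance that 40 subjects can give on safety. With 8 of 40 affected, the sentence suggests a ceiling of 33.3%, whereas the two-sided interval named just before it reaches 35.6%.

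**Working it through.** **Inputs, all from Section 9.** n = 40; 95% Clopper-Pearson; observed proportion at most 0.20, so x = 0 to 8 (0.20 × 40 = 8); stated figure 0.133. The plan does not state the sidedness of the interval. The term half-width implies two-sided, with 2.5% in each tail.

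**Formulas.**
- Two-sided lower limit L = Beta quantile(0.025; x, n − x + 1), taken as 0 at x = 0; upper limit U = Beta quantile(0.975; x + 1, n − x).
- Half-width = (U − L)/2; upper arm = U − x/n.
- One-sided 95% upper bound U₁ = Beta quantile(0.95; x + 1, n − x); excess = U₁ − x/n.
- One-sided confidence attached to observed + 0.133 = 1 − P(X ≤ x), where X is binomial(40, x/40 + 0.133).

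**Step 1: reproduce the plan's figure.** At x = 8, L = 0.09052 and U = 0.35648. The half-width is (0.35648 − 0.09052)/2 = 0.13298, which rounds to 0.133. The half-width falls as x falls, so the first sentence is right. (The Wald half-width at 8/40 is 0.124, so that is not the source.)

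**Step 2: test the second sentence under both readings.**

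| x of 40 | Observed | Half-width | Two-sided upper arm | One-sided 95% excess | Confidence at observed + 0.133 |
|---|---|---|---|---|---|
| 0 | 0.000 | 0.0440 | 0.0881 | 0.0722 | 99.7% |
| 1 | 0.025 | 0.0655 | 0.1066 | 0.0882 | 99.1% |
| 2 | 0.050 | 0.0815 | 0.1192 | 0.0992 | 98.5% |
| 3 | 0.075 | 0.0941 | 0.1289 | 0.1076 | 97.8% |
| 4 | 0.100 | 0.1044 | 0.1366 | 0.1144 | 97.2% |
| 5 | 0.125 | 0.1131 | 0.1430 | 0.1200 | 96.6% |
| 6 | 0.150 | 0.1206 | 0.1484 | 0.1247 | 96.0% |
| 7 | 0.175 | 0.1272 | 0.1528 | 0.1287 | 95.6% |
| 8 | 0.200 | 0.1330 | 0.1565 | 0.1320 | 95.1% |

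*Two-sided reading.* The upper arm stays below 0.133 at 0 to 3 of 40 and exceeds it at 4 to 8 of 40. The shortfall is 0.1366 − 0.133 = 0.0036 at 4 of 40 and 0.1565 − 0.133 = 0.0235 at 8 of 40. At 8 of 40 the arms are 0.1095 below and 0.1565 above; 0.133 is their average.

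*One-sided reading.* The excess is below 0.133 at every count from 0 to 8, and the confidence attached to observed + 0.133 never falls below 95.1%. The sentence is true as worded.

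**Step 3: look for uses of the figure.** Section 9 sizes the trial on the APHAB difference score. The only stated hypotheses concern APHAB. The termination rules in Section 18 contain no Adverse Device Effect rate. Nothing downstream takes 0.133 as an input.

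**The case for a change.** The strongest case for a change is that the one-sided reading rescues the number but not the reasoning. The plan reaches 0.133 as a two-sided half-width, and its agreement with the one-sided excess of 0.1320 looks like coincidence. Section 9 states sidedness for the primary test (one-tailed 0.025) but names no one-sided bound for safety. This is the only precision statement for a key safety endpoint in a study meant to support a 510(k) application, and the safety summary does not say which interval to report. Nor would a larger safety set remove the mismatch: with all 44 enrolled subjects, the two-sided upper arm would still be 0.1371, 0.1416 and 0.1453 at 6, 7 and 8 of 44.

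Part of this stands. The second sentence does not follow from the first at 4 to 8 of 40, and the plan does not label the bound that would make it true. The rest carries little weight:

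- The sentence describes planning precision. An analyst reporting the observed rate would compute limits from the actual count and denominator, not add 0.133 to the estimate.
- The missing interval in the safety summary is a gap that an analyst fills sensibly, because the same section already names the 95% Clopper-Pearson method for this endpoint.
- The 44-subject figures do not test a sentence that is expressly conditional on 40.

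**Conclusion.** No change to the plan follows. The half-width is correct, and the restatement is a true one-sided 95% statement over the whole range it covers; the fault is the phrase that joins them. Its largest effect is 2.3 percentage points (35.6% against 33.3% at 8 of 40), and it arises only if a reader takes the sentence as the two-sided upper limit. At 0 to 3 of 40 the statement holds under either reading. Correcting the link would leave the sample size, the hypotheses, the stopping rules and every planned analysis as they are.

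This rests on two assumptions: that the one-directional wording may fairly be read as a one-sided bound, and that any interval reported for Adverse Device Effects will be calculated from the observed data by the method Section 9 names. If the section is revised for another reason, labelling the bound as one-sided would be harmless tidying, but it would gain nothing for the trial's results.

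### Does section 9 need a pre-specified comparison of self-fit with unaided hearing, beyond self-fit against professional fit?

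*Combined protocol and SAP*

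**What the plan says.** Section 2 sets two effectiveness objectives, one on APHAB global benefit and one on QuickSIN dB SNR loss. Both concern non-inferiority of the "self-fitting method compared to the same device fit by a professional". Section 4 adds that "the professional fitting method will serve as the comparator and the control".

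Section 6 defines APHAB global benefit as a score "which is derived by subtracting the aided APHAB global score from the unaided APHAB global score". The schedule in section 8 records unaided APHAB and unaided QuickSIN once, at appointment 1, and states: "Participants will complete the QuickSiN speech test in all three conditions: unaided, aided with professional fitting, and aided with self-fitting".

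In section 9 the APHAB hypotheses concern the mean difference between self-fit and professional fit. "The observed treatment effect will be compared to the non-inferiority margin of -12.5" is the decision step, carried out with "pre-planned TEST or ESTIMATE statements using SAS PROC GLM or PROC MIXED". The QuickSIN analysis uses the same kind of crossover model, "where dB SNR loss score is the dependent variable, treatment sequence is the between-subjects factor". The only analysis sentence that covers the unaided data is general: "Unaided and both aided responses will be analyzed for each participant for the APHAB global benefit and dB SNR loss scores".

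**The concern.** A non-inferiority result against an active comparator shows that the new option is not much worse than the comparator. It shows that the new option works only if the comparator itself works by more than the margin. Here each subject has one unaided APHAB score. It enters both benefit scores and cancels when they are subtracted, so the primary contrast carries no information on benefit over unaided. The plan gives no expected professional-fit benefit to set beside 12.5. For QuickSIN the modelled variable is the aided score, so the unaided QuickSIN result enters no specified model.

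Section 1 says the study is to support the safety and effectiveness of the self-fitting method. If the report went on to say that self-fit users hear better than without a device, that statement would rest on an analysis chosen after the data were seen. The open choice between PROC GLM and PROC MIXED adds to the worry. It makes no difference to the self-minus-professional contrast with complete data, but it could change the width of an interval around mean benefit.

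**Working it through.** **Inputs from section 9:** margin -12.5, assumed true difference -5.0, SD of the difference 14, one-sided alpha 0.025, 90% power, 40 subjects with scores in both periods. **Not in the documents, so assumed:** professional-fit benefit (5 to 15 points) and the SD of self-fit benefit (10 to 25 points).

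**1. The plan's own figure.** The distance from the assumed difference to the margin is 12.5 - 5.0 = 7.5.
- Normal approximation: n = (14 × (1.960 + 1.282) / 7.5)² = 36.6, so 37.
- Noncentral t: 39 subjects give power 0.903, and 40 (two sequences of 20) give 0.910.

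The stated 40 for 90% power is reproduced with the t calculation.

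**2. What a pass means.** SE = 14/√40 = 2.214. With t(0.975, 38 df) = 2.024, the half-width is 4.48. The lowest observed difference that passes is -12.5 + 4.48 = -8.02. At an observed -5 the lower bound is -9.48.

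**3. Chance of passing if self-fit gives zero true benefit.** The true difference then equals minus the professional-fit benefit B. Power comes from the noncentral t with noncentrality (12.5 - B)/2.214 and 38 df.

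| Assumed B | P(pass) |
|---|---|
| 5 | 0.91 |
| 8 | 0.51 |
| 10 | 0.20 |
| 12.5 | 0.025 |
| 15 | 0.001 |

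A pass therefore excludes zero self-fit benefit at the nominal error rate only if B is at least about 12.5. If B is 20, a pass implies self-fit benefit above 20 - 12.5 = 7.5.

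**4. The interval for mean self-fit benefit.** With subject random, the half-width is 2.024 × SD/√40: 3.2 at SD 10, 4.5 at SD 14, 6.4 at SD 20 and 8.0 at SD 25. With subject fixed, the interval uses only the residual SD, 14/√2 = 9.90, and the half-width is 2.024 × 9.90/√40 = 3.17 whatever the SD of benefit. At zero true benefit the fixed-subject interval lies wholly above 0 in these shares of simulated trials, against a nominal 2.5%:

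| Assumed SD of benefit | Share above 0 |
|---|---|
| 10 | 2.6% |
| 14 | 7.9% |
| 18 | 13.5% |
| 20 | 16% |
| 25 | 21% |

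With equal variances, a difference SD of 14 and a benefit SD s imply a correlation of 1 - 14²/(2s²) between a subject's two benefit scores: about 0.5 at s = 14, 0.76 at 20 and 0.84 at 25. The large error rates thus depend on high correlation, which is possible but not given.

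**5. What a formal benefit rule would do.** Suppose a benefit statement were allowed whenever the subject-random 95% interval lies above 0. Unaided always comes first and is never blinded. If expectation or time moved scores by an assumed 5 points with no true benefit, the rule would be met with probability 0.87 at SD 10, 0.60 at SD 14, 0.34 at SD 20 and 0.23 at SD 25 (noncentral t, noncentrality 5√40/SD).

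**The case for a change.** The strongest case for a change is that it would cost almost nothing. The data exist, no subject or visit is added, and the primary test keeps its power. A benefit statement is foreseeable, because the endpoint is a benefit score and the study supports a 510(k) submission. Writing the interval down beforehand would remove the choice of procedure and supply the QuickSIN estimate that no planned model produces.

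Part of this stands. Section 9 names no contrast or interval against unaided, unaided QuickSIN enters no specified model, and a bare pass is not evidence of benefit over unaided. The rest is weaker:

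- The plan proposes no claim over unaided. The harm depends on a statement that the documents do not make.
- For APHAB the endpoint definition already fixes the estimate. Only an interval around a treatment mean is left, and section 9 commits to analysing the unaided responses.
- Section 9 calls the analysis a mixed model and names a random effect for subject within sequence, though in the sentence on carryover. A statistician following it would fit subject as random, so the fixed-subject interval is an unlikely reading.
- For QuickSIN, the unaided-minus-aided difference is the obvious summary, with little room for selective choice.
- Pre-specification would not cure the main weakness of the unaided comparison, which is its fixed order and lack of blinding.

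**Conclusion.** The gap is real but does not call for a change. The non-inferiority test, the margin's role in it and the 40 evaluable subjects (power 0.91) answer the objectives in section 2, and none of them depends on the unaided comparison. What is missing is the detail of a supportive description that analysts can fill sensibly: mean unaided-minus-aided benefit for each fitting with a 95% interval, subject random, read as a before-after comparison. A pass should be read as non-inferiority to professional fitting and no more.

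How far a pass also speaks to benefit over unaided turns on professional-fit benefit. Across an assumed 5 to 15 points, the chance of passing with zero self-fit benefit runs from 91% to 0.1%, so the documents do not settle the size of the problem. The procedure choice matters only for an interval that the plan does not define, and its effect spans about 3% to 21% over assumed SDs of 10 to 25. Adding a formal benefit rule would create a claim that the plan does not have, one that an assumed 5-point shift alone would satisfy in 23% to 87% of trials.

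### Does naming SAS TEST or ESTIMATE statements for the primary analysis mean that the -12.5 margin is never actually tested?

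*Combined protocol and SAP*

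**What the plan says.** Section 9 (Statistical design and analysis) sizes the trial to show "the non-inferiority against the margin of -12.5 using Mixed Model ANOVA, setting one-tailed" alpha of 0.025, assuming that the mean self-minus-professional difference "is -5.0, and the standard deviation of the difference score is 14". It states the null hypothesis as a difference below -12.5 and the alternative as a difference at or above -12.5. It then says "The observed treatment effect will be compared to the non-inferiority margin of -12.5 by way of pre-planned TEST or ESTIMATE statements", in either PROC GLM or PROC MIXED. It gives no confidence level or success criterion at that point.

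The model is described as one "where APHAB score is the dependent variable, treatment sequence is the between-subjects factor". Section 6 (Endpoints) defines the primary endpoint as the APHAB global benefit score, "which is derived by subtracting the aided APHAB global score from the unaided APHAB global score", so higher benefit is better and a higher aided score is worse.

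**The concern.** Three features look wrong when read together.

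- **Software statements.** As general SAS behaviour (the documents do not discuss it), an ESTIMATE statement prints a t-test of a zero contrast, and a TEST statement in PROC GLM gives an F-test of no effect. Neither p-value refers to -12.5. With no confidence bound named, comparing the observed effect with the margin could even be taken as a comparison of the bare point estimate.
- **Hypotheses.** Equality sits in the alternative, so a true difference exactly at the margin would count as non-inferior.
- **Outcome wording.** The model sentence and the definition of the means say APHAB score without the word benefit. On the raw aided scale, a margin of -12.5 would lie on the wrong side.

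This is the only decision on which the primary claim rests, and Section 1 says that the trial is meant to support a 510(k) application. A rule that did not test the margin at 0.025 would be serious.

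**Working it through.** **Inputs, all from Section 9:** margin -12.5; assumed difference -5.0; SD of the within-subject difference 14; 40 subjects with scores in both periods; one-tailed alpha 0.025; power 90%. Section 8 gives 1:1 allocation to the two orders of fitting.

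**1. Reproduce the sample size.** The distance from the assumed difference to the margin is -5 - (-12.5) = 7.5.

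- Normal approximation: n = [14 × (1.960 + 1.282) / 7.5]² = 36.6, so 37.
- Noncentral t: 38 subjects give 89.5% power and 39 give 90.3%, so 39.
- The next even number, for two equal sequences, is 40. Power at 40 is 91.0% (t, 38 df).

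The stated 40 is therefore the size for a one-sided 0.025 test against -12.5.

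**2. Get that test from an ESTIMATE contrast.** At n = 40, SE = 14/√40 = 2.214 and t(0.975, 38 df) = 2.024.

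- Shifted statistic: t = (estimate + 12.5)/SE.
- Equivalent interval rule: estimate - 2.024 × SE > -12.5.
- Smallest passing estimate: -12.5 + 2.024 × 2.214 = -8.02.
- Size at a true difference of -12.5: 0.025. Power at -5: 91.0%.

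In 100,000 simulated trials at the margin, the shifted t and the interval rule never disagreed, and the rejection rate was 0.0249.

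**3. Compare the two p-values for an observed difference of -5 with SE 2.214.**

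- Against zero: t = -5/2.214 = -2.26, two-sided p = 0.030.
- Against -12.5: t = 7.5/2.214 = 3.39, one-sided p = 0.0008, with 95% lower limit -5 - 4.48 = -9.48.

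The default p-value answers another question, but the contrast and standard error are enough for the right one.

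**4. Size of the alternative readings (n = 40, SD 14).**

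| Rule | Result | Fits Section 9? |
|---|---|---|
| 95% lower limit, or shifted t, against -12.5 | size 0.025; power 91.0% at -5 | Yes |
| 90% lower limit against -12.5 | size 0.050 | No: alpha is 0.025, one-tailed |
| Point estimate against -12.5 | 50% false positives at the margin | No: uses no alpha |
| Test of zero | self-fit significantly worse in 59.5% of trials at -5 | No: hypotheses are set at -12.5 |

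**5. Equality sign.** The estimate is continuous. The rejection probability is 0.02500 at a true difference of -12.5 and 0.02500 at -12.5001. The critical value and power do not move.

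**6. Scale.** The sentence that calls the outcome the APHAB score opens by comparing the global benefit scores under the two fittings. The symbols used to define the means first appear in the sample-size paragraph, directly after it names the difference in global benefit scores. The objective in Section 2, the endpoint in Section 6 and the imputation paragraph of Section 9 all name benefit. The sign agrees too: Section 8 records the unaided APHAB once, so (unaided - aided self) - (unaided - aided professional) = -(aided self - aided professional). A negative value means that self-fitting does worse, which is the only scale on which an assumed -5 and a margin of -12.5 describe tolerated loss.

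**The case for a change.** The best argument for a change is that a primary decision rule should be explicit before data are seen. Section 9 never states a success criterion, and alpha appears only in the sample-size paragraph. The choice of statement and procedure is left open, and an F-test of no effect carries neither direction nor margin. An observed difference between -12.5 and -8.02 would pass a point-estimate rule and fail the interval rule. A sentence of clarification would cost almost nothing.

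Much of that is accurate. The criterion is unwritten, TEST is ill suited to the purpose, and the inequality signs are unconventional. What does not follow is that the choice is open. A point-estimate rule, a 90% limit and a zero-null p-value each contradict something that Section 9 states: the hypotheses at -12.5, the one-tailed 0.025, or both. TEST is offered only as an alternative to ESTIMATE, which serves. The plan also combines imputed data sets by Rubin's rules, which pool an estimate and its standard error, again leading to a contrast with its interval. Rewriting the sentences would describe the same test.

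**Conclusion.** The concern does not call for a change. Section 9 gives the margin, direction, alpha, sidedness, hypotheses and model, and together they determine one test: the lower limit of a two-sided 95% interval for self minus professional benefit against -12.5, or the equivalent shifted t. That test has size 0.025 and 91.0% power at 40 subjects, so the planned sample size stands. The figures of 50% and 59.5% belong to rules that the plan does not contain, and the wrong-scale reading is excluded by the plan's own text. What survives is missing detail that a competent analyst fills correctly, plus a notation slip with no numerical effect.

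This rests on the plan's assumed SD of 14 and difference of -5, on complete pairs with 38 degrees of freedom (pooling over imputations would alter the degrees of freedom slightly), and on the analysis being done by an experienced biostatistician, as Section 9 requires.
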